**Development and external validation of an international, multicenter machine learning algorithm for prediction of surgical outcome after microsurgery for unruptured intracranial aneurysms****The *Prediction of adverse events after microsurgery for intracranial unruptured aneurysms (PRAEMIUM)* study**[name], BMed; [name], MD; [name], MD;*ClinicalTrials.gov:*ID: PRAEMIUM    *Prediction of Outcomes After Surgery for Unruptured Intracranial Aneurysms*    NCT04819074*1: Department of Neurosurgery & Machine Intelligence in Clinical Neuroscience (MICN) Laboratory, Clinical Neuroscience Center, University Hospital Zurich, University of Zurich, Switzerland***Introduction**

Unruptured intracranial aneurysms (UIAs) are incidentally detected at an increasing rate, mostly owing to the rise in availability of non-invasive cranial imaging. Decision-making in UIAs is complex and requires consideration of many risk factors for aneurysm growth and rupture to balance the benefits and risks of treatment versus observation. This is due to: 1) the high morbidity and case fatality inherent to aneurysmal subarachnoid hemorrhage (SAH) 2) the relatively low rupture rate of unruptured aneurysms; 3) the potential morbidity and mortality rate associated with either microsurgical or endovascular treatment.

Some consistent risk factors for rupture have been identified, including involvement of the posterior circulation, larger diameter, higher age, and some specific populations such as Japanese and Finnish patients. Many other risk factors have been suggested based on varying levels of evidence. However, it is difficult to integrate this considerable number of factors into a single risk assessment and to present a clear clinical decision making algorithm to patients. A range of scoring systems have been developed and validated to approximate the risk of rupture (PHASES) and growth (ELAPSS), or to balance the risks and benefits of microsurgical treatment versus follow-up imaging directly (UIATS) by integrating some of these risk factors. Still, these scores are focused on predicting rupture events instead of neurological outcome. In addition, they usually are focused on solely one outcome, instead of providing a wide range of objective predictive analytics that may then improve shared decision-making.

Machine learning (ML) methods have been extraordinarily effective at integrating many clinical patient variables into one holistic risk prediction tailored to each patient. We have conducted a pilot study to assess the feasibility of predicting surgical outcomes after surgery for UIAs in a small single-center sample. We found that prediction was feasible with good performance metrics, and also identified the most important factors to be included in such models. To the authors' best knowledge, a robust, multicenter, externally validated prediction model or predictive score for surgical outcome after microsurgery for UIAs does not yet exist.

Accurate preoperative identification of patients at high risk for adverse outcomes would be clinically advantageous, as it would allow enhanced resource preparation, better surgical decision-making, enhanced patient education and informed consent, and potentially even modification of certain modifiable risk factors. The aim of the *Prediction of adverse events after microsurgery for intracranial unruptured aneurysms* (PRAEMIUM) study is therefore to develop and externally validate a clinically applicable, robust ML-based prediction tool based on multicenter data from a range of international centers.

## Methods

### Overview

Data will be collected by a range of international centers. Overall, the model will be built and publication will be compiled according to the transparent reporting of a multivariable prediction model for individual prognosis or diagnosis (TRIPOD) guidelines.

The University Hospital Zurich (USZ) center is the sponsor of the PRAEMIUM study.

**(Sponsor:** [name]. [name]; **Principal Investigators:** PD Dr. med. [name], [name])

### Ethical Considerations

Each center will be responsible for their own ethics board / institutional review board (IRB) approval. They must gain approval for retrospective or prospective data collection and sharing of the completely anonymized data with the sponsor. They must also organize a data use agreement to the sponsor institution. The sponsor can aid by providing said protocol and data use agreement, which will also be registered online on ClinicalTrials.gov.

### Inclusion and Exclusion Criteria

We will include all adult patients (18 years or older) undergoing microsurgical treatment for UIAs. No specific exclusion criteria will be set. Patients with prior SAH may only be included when surgical treatment occurred at least 4 weeks after ictus. **Only patients treated from January 1st 2010 onwards can be included in this study.**

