### Endpoint Definitions

Models will be developed for the following three endpoints at discharge: **Poor neurological outcome** (1), as well as presence of (2) **new sensorimotor neurological deficits** and (3) any **complications** (surgical or non-surgical). Neurological outcome was assessed by the modified Rankin scale (mRS), and a favorable neurological outcome was defined as mRS 0, 1, or 2. Complications will be assessed using the modified 2009 Clavien-Dindo grading (CDG), and occurrence of a complication was defined as any deviation from CDG 0. The Clavien-Dindo grading system is a classification of surgical complications: Grad 0 signifying no complication, Grade I identifying complications with any deviation from the normal intra- or postoperative course requiring medical treatment, and so forth. Detailed definitions are provided in the Excel spreadsheet. Surgery-related as well as none-surgery-related complications are counted. In case of multiple complications, only the complication with the highest CDG was counted per patient.

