### Input Feature Definitions

All features are measured preoperatively. Recorded baseline variables will include age, gender, maximum aneurysm diameter, anatomical location (artery), total number of aneurysms per patient, if multiple aneurysms were treated

during the index session, calcification of the aneurysm wall or neck, aneurysm morphology (saccular, dissecting, fusiform, or other), involvement of critical perforating or branch vessels, and intraluminal thrombosis.

We will also capture prior SAH, mRS at admission, prior aneurysm treatment, presence of anticoagulation/antiplatelet therapy preoperatively, and hypertension, as well as American Society of Anesthesiologists (ASA) grading, the PHASES, ELAPSS, and UIATS scores including the UIATS “pro-repair” and “pro-conservative treatment” subscores. The unruptured intracranial aneurysm treatment score (UIATS) consists of two subscores: One that represents the strength of recommendation for invasive repair of an unruptured aneurysm, and one that represents the strength of recommendation for conservative management of an unruptured aneurysm. The final overall UIATS score is subsequently calculated as the difference between the two subscores. Also included was the surgical approach: minimally invasive or standard approach, and whether a bypass was performed.

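### The SAH interval ends at surgery but baseline mRS is taken at admission, so decline before a late same-stay operation is scored as poor outcome (endpoint 1) with no predictor to account for it

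*Combined protocol and SAP*

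**What the plan says.** Four parts of the Methods bear on this point.

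- **Inclusion and Exclusion Criteria.** The population is set by "We will include all adult patients (18 years or older) undergoing microsurgical treatment for UIAs", followed by "No specific exclusion criteria will be set". The one restriction on earlier haemorrhage is "Patients with prior SAH may only be included when surgical treatment occurred at least 4 weeks after ictus". Nothing requires a separate admission or a discharge after the SAH, and there is no limit on disability before surgery.
- **Input Feature Definitions.** The general timing rule is "All features are measured preoperatively". The specific baseline item is given in "We will also capture prior SAH, mRS at admission, prior aneurysm treatment". The section does not say which admission is meant.
- **Endpoint Definitions.** The time point is given by "Models will be developed for the following three endpoints at discharge". Endpoint 1 is read off the scale directly: "a favorable neurological outcome was defined as mRS 0, 1, or 2". It is not a change from baseline. Endpoint 2 concerns sensorimotor deficits that are *new*, with no reference time stated. Endpoint 3 uses Clavien-Dindo grades, described as departures from the expected course during or after the operation, and "Surgery-related as well as none-surgery-related complications are counted".
- **Data Collection.** Entries are anonymised and renumbered so that they cannot be linked back to patients.

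**The concern.** The eligibility interval closes at surgery, while the observation window runs from admission to discharge. For an elective patient this makes little difference, because admission and surgery are close together. For a patient still in hospital after an SAH, the two can be 4 weeks or more apart, and a great deal can happen neurologically in that time. Decline in that gap is too late to appear in the baseline predictor and too early to be caused by the operation, yet it is present at discharge and scored there.

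The Introduction says the tool is meant to support surgical decisions and informed consent. Misattributed events would sit among patients with prior SAH. A model that uses prior SAH as a predictor could then assign too high a surgical risk to someone with a remote SAH who is admitted electively.

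The listed variables include prior SAH but no interval from ictus to surgery, no marker for a same-stay operation and no mRS immediately before surgery. On those variables the sponsor could not find the affected patients afterwards. If the validation centres use the same definitions, external validation would not expose the problem either.

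**Working it through.** **1. Timing, side by side**

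| Item | Clock or time point | Section |
|---|---|---|
| SAH interval | ictus to surgery, at least 4 weeks | Inclusion and Exclusion Criteria |
| Baseline mRS | admission | Input Feature Definitions |
| Endpoint 1 | absolute mRS at discharge; poor = not 0 to 2 | Endpoint Definitions |
| Endpoint 2 | discharge; reference for *new* not stated | Endpoint Definitions |
| Endpoint 3 | intra- or postoperative events | Endpoint Definitions |

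**2. A hypothetical patient traced through the rules.** Day 0: admitted with SAH at mRS 1, and the ruptured aneurysm is secured. Day 8: a stroke leaves hemiparesis and mRS 4. Day 30, same stay: a second, unruptured aneurysm is operated on. Discharge: mRS 4.

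- Eligible: day 30 is more than 28 days after ictus, and the operation is for an unruptured aneurysm.
- Baseline predictor: mRS 1.
- Endpoint 1: positive, because mRS 4 is outside 0 to 2.
- Endpoint 2: positive if *new* means since admission; negative if it means since the pre-operative examination.
- Endpoint 3: the day-8 stroke is neither intra- nor postoperative, so it should not count.

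Now take a patient readmitted at mRS 4 some time after an SAH and discharged at mRS 4. Endpoint 1 is again positive, because it is an absolute score, but admission mRS is 4 and the model can use it. What the timing adds is specifically the decline between admission and surgery that the predictor misses.

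**3. The plan's own figures (Sample Size).** Patients = events / incidence.

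- Training: 250 / 0.10 = 2500.
- Validation: 150 / 0.10 = 1500.
- Total: 2500 + 1500 = 4000 patients, with 250 + 150 = 400 events.

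These reproduce the plan exactly, and the point does not alter them.

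**4. Possible size.** Let s be the share of patients operated on late in an SAH stay, and q the share of those at mRS 3 or worse before surgery and still so at discharge. Neither is in the documents. The assumed ranges are s = 0.25% to 5% and q = 20% to 60%.

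- Carried-over events = 4000 × s × q.
- Observed incidence, if 10% is the rate apart from carried-over events: (1 − s) × 0.10 + s × [q + (1 − q) × 0.10] = 0.10 + 0.90 × s × q.

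| s | q | Patients (4000 × s) | Carried-over events | Share of 400 | Observed incidence |
|---|---|---|---|---|---|
| 0.25% | 20% | 10 | 2 | 0.5% | 10.045% |
| 1% | 40% | 40 | 16 | 4% | 10.36% |
| 2% | 40% | 80 | 32 | 8% | 10.72% |
| 5% | 60% | 200 | 120 | 30% | 12.70% |

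These counts are ceilings for the gap itself, because q includes patients already at mRS 3 or worse on admission, whose disability the predictor records.

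**5. Concentration.** If prior-SAH patients are a fraction p of the cohort, the rise in observed incidence within that group is 0.90 × s × q / p, larger than the overall rise by a factor of 1/p. The documents do not give p, so this cannot be turned into a number.

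**The case against.** The strongest reply is that pre-operative disability counts in endpoint 1 because the endpoint is an absolute score, wherever the SAH interval is anchored. That is correct, and it narrows the point: what is lost is the predictor's ability to account for decline between admission and surgery. It does not remove the point, because being preoperative does not make admission mRS current.

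The second reply is that the detailed definitions are in the Excel spreadsheet, which is not among the documents and may fix the reference time for *new*. That stands for endpoint 2, and is why the claim there is conditional. Eligibility and the time point of baseline mRS are set in the protocol itself. If *admission* means the stay for the operation, nothing changes for a same-stay patient, since the two admissions are one.

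Several stronger readings are tempting but not supported:

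- *All three endpoints absorb SAH damage.* Certain only for endpoint 1. Endpoint 3 is worded around the intra- and postoperative course. SAH sequelae arising after the operation could count, since non-surgical complications are included, but those are not damage present beforehand.
- *The ruptured aneurysm itself could be enrolled once 4 weeks have passed.* The criteria limit inclusion to treatment of unruptured aneurysms, and the SAH sentence qualifies that population.
- *Some 10 to 40 events are misclassified.* This follows from assuming 0.5% to 2% of 4000 (20 to 80 patients) with half discharged at mRS 3 to 6; as a share of 400 it is 2.5% to 10%. It also counts patients already disabled at admission and patients harmed by the operation, so it does not measure this mechanism.
- *The tool will overstate risk after remote SAH.* The algorithm is not yet chosen, features may be eliminated and the size of the subgroup is unknown. *Could* is as far as the documents go.
- *The interval was meant to keep SAH effects out.* Plausible, but the protocol gives no rationale.

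**Conclusion.** The point holds in a limited form. The text admits a patient operated on for an unruptured aneurysm late in an SAH stay. For that patient, decline to mRS 3 or worse between admission and surgery that persists to discharge is scored as a poor outcome while the baseline predictor shows the better, earlier state. This is firm for endpoint 1, conditional on the meaning of *new* for endpoint 2, and largely absent for endpoint 3.

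The size is unknown. The range of 2 to 120 events rests wholly on the assumed s and q, and the documents cannot say whether the overall effect is negligible or material. Any effect would be concentrated in the prior-SAH subgroup and could raise predicted risk there. The change is worth making because it is cheap and the error could not be repaired from the anonymised data, not because a large bias has been shown. The planned sample size is unaffected.

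**What to change.** Make the change before data entry, in one of two ways.

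- **Preferred.** In Input Feature Definitions, replace mRS at admission with the last mRS before the index operation. In Endpoint Definitions, define new sensorimotor deficits relative to that same pre-operative status. Put both into the spreadsheet instructions. Endpoint 1 remains an absolute score, but the predictor then carries whatever happened before surgery. The cost is some extra abstraction for patients whose status changed between admission and surgery; for ordinary elective patients the recorded value should be essentially the same.
- **Alternative.** In Inclusion and Exclusion Criteria, keep the 4-week length but require that the admission for the index operation began at least 4 weeks after ictus. The cost is the loss of a small number of same-stay patients. The reference time for *new* should still be stated.

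Neither version needs a clause about which aneurysm caused the SAH. The criteria already restrict the study to unruptured aneurysms, and such a clause could remove patients with a previously ruptured and treated aneurysm, changing the population.

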### Authorship

Each center must contribute data from at least 100 patients to be included. Each eligible institution designates 1 primary author per center who will be included in the primary author list. Each eligible center may also designate 2 additional secondary authors, who will be included in the author list as part of the PRAEMIUM study group, and who

will be fully indexed in PubMed as contributing authors. The sponsor institution is entitled to 3 primary authors and to 4 secondary authors.

### Data Collection

Each center will collect their data either retrospectively, or from a prospective registry, or from a prospective registry supplemented by retrospectively collected variables. Data from patients operated from January 1st 2010 and onwards will be eligible for inclusion. **Data collection should be completed, and anonymized data should be sent to the sponsor institution ([[contact]](mailto:[contact])) by 1st of August 2021.**

A standardized Excel spreadsheet will be provided by the sponsor. The data will be entered in standardized and anonymized form. This spreadsheet will only contain a study-specific patient number. The data set is anonymized source data that includes clinical data extracted from electronic health records (retrospectively or from a prospective registry of already existing data). The data will be anonymized upon entering them into the PRAEMIUM Excel spreadsheet, after which the patients will be numbered consecutively and there will be no way to trace the data back to individual patients. No identifiable data such as date of birth will be included. Whenever the PRAEMIUM Excel spreadsheet is transferred, it will be encrypted using a password and sent through a secure institutional e-mail server to **[contact]**. The password will be sent in a separate e-mail. Some missing data is acceptable, but should be kept to a minimum (i.e. must be < 10%)

### Endpoint Definitions

Models will be developed for the following three endpoints at discharge: **Poor neurological outcome** (1), as well as presence of (2) **new sensorimotor neurological deficits** and (3) any **complications** (surgical or non-surgical). Neurological outcome was assessed by the modified Rankin scale (mRS), and a favorable neurological outcome was defined as mRS 0, 1, or 2. Complications will be assessed using the modified 2009 Clavien-Dindo grading (CDG), and occurrence of a complication was defined as any deviation from CDG 0. The Clavien-Dindo grading system is a classification of surgical complications: Grad 0 signifying no complication, Grade I identifying complications with any deviation from the normal intra- or postoperative course requiring medical treatment, and so forth. Detailed definitions are provided in the Excel spreadsheet. Surgery-related as well as none-surgery-related complications are counted. In case of multiple complications, only the complication with the highest CDG was counted per patient.

### Input Feature Definitions

All features are measured preoperatively. Recorded baseline variables will include age, gender, maximum aneurysm diameter, anatomical location (artery), total number of aneurysms per patient, if multiple aneurysms were treated

during the index session, calcification of the aneurysm wall or neck, aneurysm morphology (saccular, dissecting, fusiform, or other), involvement of critical perforating or branch vessels, and intraluminal thrombosis.

We will also capture prior SAH, mRS at admission, prior aneurysm treatment, presence of anticoagulation/antiplatelet therapy preoperatively, and hypertension, as well as American Society of Anesthesiologists (ASA) grading, the PHASES, ELAPSS, and UIATS scores including the UIATS “pro-repair” and “pro-conservative treatment” subscores. The unruptured intracranial aneurysm treatment score (UIATS) consists of two subscores: One that represents the strength of recommendation for invasive repair of an unruptured aneurysm, and one that represents the strength of recommendation for conservative management of an unruptured aneurysm. The final overall UIATS score is subsequently calculated as the difference between the two subscores. Also included was the surgical approach: minimally invasive or standard approach, and whether a bypass was performed.

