### Predictive Modeling

A KNN imputer will be co-trained to impute any missing data that may occur in future application of the model. If there is missing data in the training set, it will be imputed using said KNN imputer. Features or patients with a missingness greater than 25% will be excluded. Data will be standardized and one-hot-encoded. In case of major class imbalance – which is expected for the abovementioned endpoint – random upsampling or synthetic minority oversampling (SMOTE) will be applied to the training set. All features will initially be provided to the model for training. If necessary, we will apply recursive feature elimination (RFE) to select input features on the training data.

We will trial the following algorithms for binary classification: Generalized linear model (GLM), generalized additive model (GAM), stochastic gradient boosting machine (GBM), naïve Bayes classifier, artificial neural network, support vector machine (SVM), and random forest. Each model will be fully trained and hyperparameter tuned where applicable. The final model will be selected based upon AUC, sensitivity, and specificity, as well as calibration metrics on the resampled training performance. Training will occur in repeated 5-fold cross-validation with 10 repeats.

The one final model will then be assessed on the external validation data only once. 95% confidence intervals for external validation metrics will be derived using the bootstrap.

The threshold for binary classification will be identified on the training data alone using the AUC-based “closest-to-(0,1)-criterion” or Youden’s index to optimize both sensitivity and specificity. All analyses will be carried out in R Version 3.6.2.

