### Interpretability

The degree and choice of methods for interpretability will depend on the finally chosen algorithm. Some algorithms can natively provide explanations as to which factors influence the outcome in what way. Thus, in case e.g. a GLM, GAM, or naïve Bayes classifier is chosen, the parameters / partial dependence values will be provided. For simple decision trees, diagrams of the decision-making process can be provided. Other models with higher degrees of complexity, such as neural networks or stochastic gradient boosting machines cannot natively provide such explanations. In that case, we will provide both AUC-based variable importance as well as model-agnostic local interpretations of variable importance using the LIME principle.

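### The UIATS total is listed as a model input beside the two subscores that define it: the three UIATS coefficients of an unpenalized GLM lose a unique solution, and naive Bayes can count the same evidence twice

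*Combined protocol and SAP*

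**What the plan says.** All places are in the combined protocol and SAP.

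- **Input Feature Definitions** lists, among the recorded baseline variables, the PHASES, ELAPSS and UIATS "scores including the UIATS “pro-repair” and “pro-conservative treatment” subscores". It then defines the total: "The final overall UIATS score is subsequently calculated as the difference between the two subscores".
- **Predictive Modeling** states: "All features will initially be provided to the model for training". Preprocessing is described as "Data will be standardized and one-hot-encoded". A later reduction is optional: "If necessary, we will apply recursive feature elimination (RFE) to select input features on the training data". The seven candidate algorithms include a GLM, for which no penalty is stated, and a naive Bayes classifier.
- **Interpretability** says that if a GLM, GAM or naive Bayes classifier is chosen, "the parameters / partial dependence values will be provided".

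Nowhere does the plan drop one of the three UIATS terms, say how aliased terms are handled, or require the total to be recomputed from the subscores after KNN imputation.

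**The concern.** The third UIATS feature is an exact linear function of the other two and adds no information. Two of the planned outputs are exposed to this.

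The first is the published parameters. An unpenalized GLM cannot separate three terms that span only two dimensions. Software will usually drop one, and the coefficients of the remaining two depend on which. A reader of the paper could take the sign of a UIATS coefficient as a finding when it is a by-product of column order.

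The second is the calibration of naive Bayes. That method treats features as independent within each outcome class, so a derived feature can enter the same evidence again and push the predicted risks too far apart. The Evaluation section treats calibration as of central importance, and calibration is one of the criteria for choosing the final model.

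**Working it through.** **The plan's own figure.** Sample Size asks for 250 events at about 10% incidence: 250 / 0.10 = 2500 for training. Validation adds 1500 patients, or 1500 × 0.10 = 150 events. The total is 2500 + 1500 = 4000, as stated. Nothing below changes it; it supplies the training size for the simulations.

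**Step 1: GLM.** Write R for the pro-repair subscore, C for the pro-conservative subscore and D = R − C for the total. Standardizing does not break the dependence: zD = (sR·zR − sC·zC) / sD, where s is the standard deviation (SD).

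Simulated check, with values assumed because the plan gives none: 2500 patients, 223 events, SDs 4 and 3, correlation −0.3 and two further covariates. The design matrix has 6 columns and rank 5. Dropping each term in turn gives these standardized coefficients:

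| Dropped | R | C | D | Other two covariates | Deviance |
|---|---|---|---|---|---|
| R | – | 0.493 | −0.154 | 0.286, 0.545 | 1363.600 |
| C | 0.648 | – | −1.088 | 0.286, 0.545 | 1363.600 |
| D | −0.107 | 0.574 | – | 0.286, 0.545 | 1363.600 |

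The rows are one model written three ways. With sD = √(16 + 9 + 2 × 0.3 × 12) = 5.67, the third row converts to the second: R becomes −0.107 + 0.574 × 4/3 = 0.658, and D becomes −0.574 × 5.67/3 = −1.085. The small differences from the table arise because sample SDs are not exactly 4 and 3. Fitted probabilities differ by at most 2 × 10⁻¹⁵. The coefficient for R changes sign although the fit is identical.

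If totals were imputed separately from the subscores, the dependence would become near-exact instead of exact. With noise (SD 3, assumed) added to 5% of totals, the variance inflation factors were 37.4 (R), 22.4 (C) and 77.0 (D), so the coefficients would remain unstable.

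**Step 2: why direction matters in naive Bayes.** Take R and C as normal with common SD s, uncorrelated within class, with mean differences dR and dC between patients with and without the event. Naive Bayes gives each feature the weight (mean difference) / variance. The total has mean difference dR − dC and variance 2s². Adding it changes the weights to

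- wR = (1.5·dR − 0.5·dC) / s², where dR / s² would be correct;
- wC = (1.5·dC − 0.5·dR) / s², where dC / s² would be correct.

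The calibration slope is (wR·dR + wC·dC) / [s²(wR² + wC²)]. With UIATS features only:

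- opposite directions (dR = d, dC = −d): (2 + 2) / (4 + 4) = 0.5;
- only one acts (dC = 0): 1.5 / (2.25 + 0.25) = 0.6;
- same direction (dR = dC): (1 + 1) / (1 + 1) = 1.0.

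A slope below 1 means predictions that are too extreme. Other predictors in the model dilute these falls.

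**Step 3: naive Bayes simulations.** Gaussian naive Bayes, 2500 training and 20,000 new patients, 60 replicates per setting, 8% to 10% events, two other covariates. The subscores act in opposite directions, with log-odds per SD of −0.5β for R and +β for C. Mean calibration slope, two subscores → all three terms:

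| Correlation of R and C | β = 0 | β = 0.3 | β = 0.6 |
|---|---|---|---|
| −0.3 | 0.90 → 0.82 | 0.87 → 0.61 | 0.87 → 0.52 |
| 0 | 0.90 → 0.83 | 0.94 → 0.69 | 1.02 → 0.62 |
| +0.3 | 0.91 → 0.84 | 0.95 → 0.79 | 1.04 → 0.73 |

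A further set, also with 2500 training patients, varied the direction of effect:

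| Assumed effect of the subscores | Slope without total | Slope with total | Change |
|---|---|---|---|
| Opposite directions | 0.90 | 0.59 | −0.31 |
| Only one acts | 0.88 | 0.73 | −0.15 |
| Same direction | 0.91 | 0.89 | −0.02 |
| No effect | 0.83 | 0.79 | −0.04 |
| Opposite, UIATS overlapping other features (two settings) | 0.70; 0.60 | 0.51; 0.46 | −0.19; −0.14 |

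In neither table did the slope improve when the total was added.

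**The case against.** The strongest reply is that the study aims at prediction, not at estimating UIATS effects, and that GLM predictions do not change at all. This stands. A reader might infer that the GLM as a whole is unidentifiable or predicts worse; Step 1 shows that only the three UIATS coefficients are affected, and they are published only if such a model is chosen.

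A reader might also infer that naive Bayes must become overconfident, or that the comparison of algorithms is distorted. The plan does not support either as a general statement. It gives no direction or size of effect for either subscore, and in the same-direction and no-effect settings the fall is small. Naive Bayes is one of seven candidates, and selection uses calibration as well as AUC, sensitivity and specificity, so a poorly calibrated version may simply not be chosen.

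A third argument is that age, diameter, location and the other scores already overlap with UIATS, so naive Bayes independence fails anyway and removing the total gains nothing. One simulation with scores built partly from other features did give a slope of 0.29 with and without the total. That does not generalize: overlap lowered the slope, but with opposite directions the total still lowered it further in both overlap settings of Step 3.

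A fourth argument is that the planned upsampling or SMOTE would do more to calibration. Balancing to 50% (assumed) gave a mean predicted-to-observed risk of about 4.7 to 5.6 whether or not the total was included. That is a fair reminder that the slopes above come from a pipeline without resampling; it is no reason to keep a redundant feature.

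Recursive feature elimination might remove one term, but it has no stated trigger. Over-weighting of UIATS in KNN or SVM distances, and splitting of its variable importance, might also be suspected. Neither was quantified, and AUC-based importance computed feature by feature would not be split, so neither is claimed here.

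**Conclusion.** The point holds in a limited form. The plan's own definition makes the three UIATS inputs linearly dependent, and nothing in it reliably removes the redundancy. For an unpenalized GLM the consequence is certain but narrow: the UIATS coefficients are arbitrary up to the choice of dropped term, while predictions, discrimination, calibration and all other coefficients are unchanged. A penalized GLM would give a unique solution, but none is specified.

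For naive Bayes the consequence is conditional. The slope falls materially if the subscores act in opposite directions, moderately if only one acts, and little otherwise. These figures rest on assumed distributions, correlations and effect sizes, on Gaussian naive Bayes, and on no resampling. Severity is low: this is a free improvement, not a threat to the study.

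**What to change.** In Input Feature Definitions, state that only the two UIATS subscores enter the models. If the total is reported descriptively, compute it from the subscores after imputation and do not use it as a feature.

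The cost is one line in the feature list. The total is a function of the subscores, so no information is lost, no new data are needed, and the sample size stays as planned. The change gives the UIATS terms unique GLM coefficients as far as this dependence is concerned, removes this source of double counting in naive Bayes, and ensures that any reported total equals the difference of its parts. It does not address the overlap between UIATS and the other features.
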